### *Modeling Issues and Sensitivity Analyses.*

Sensitivity analyses will include predictors that are predictive of missing visits or whose average levels differ across study arms. Predictors predictive of missingness are likely to occur; satisfactory randomization should prevent average predictor levels from differing across intervention groups. We will analyze missing visits as a binary outcome with logistic random intercept regression model as functions of key (baseline; time-fixed) predictors (for example: Baseline behavior (e.g. whether they had tested for HIV in the 3 months prior to baseline), age under 30 vs. 30+; type of SUD; ASAM Level I & II vs. III & IV; stimulant user vs. not; race/ethnicity; preferred substance, education level), prior to performing the final analysis. Variables that are significant predictors of missing visits will be included as predictors in sensitivity analyses of intervention effects. If substantial missingness occurs in key baseline predictors, we will use multiple imputation to fill in the missing predictors. The missing visit analysis omits the baseline time point, as the baseline observation is required. To evaluate randomization, we analyze the key baseline predictors as outcomes in a one-way ANOVA. If some of the predictors differ by intervention arm, they will be included in sensitivity analyses.

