Determine the effectiveness of the intervention compared with the standard-of-care in achieving the following:

1) PrEP-related outcomes following jail release (PrEP continuum of care):

- a) establish a primary care provider, who can prescribe PrEP,
- b) obtain screening for PrEP,
- c) begin PrEP,
- d) adhere to PrEP, and
- e) remain on PrEP for at least 3 months.

2) Infection and prevention screening tests in the community:

- a) HIV every 3 months,
- b) bacterial STIs every 6 months; and
- c) HCV at least once.

3) Obtaining and remaining engaged in treatment for substance use disorders (SUDs) in the community, according to each participant's recommended American Society of Addiction Medicine level of care.

Participant-related Study Methods

Overview

A total of 266 HIV-negative or HIV status unknown men who have sex with men (MSM) and transgender women (TGW) will be enrolled in this randomized controlled trial prior to being released from Men's Central Jail. Participants will be recruited from a unit of the jail that is designated as protective custody for self-identified gay and bisexual men and for transgender women. Participants will be randomized into either the standard-of-care condition or the intervention condition that involves an innovative new GPS-based mobile app and incentives for utilization of prevention-related services, in addition to the support of a Peer Mentor (app+incentives+PM). Each condition will include up to 150 participants. The standard-of-care condition will consist of the substance-abuse focused transitional case management and referral services provided by the LA Center for Alcohol and Drug Abuse's **Substance Treatment And Re-entry Transition program (Project START Program)**

1. Recruitment and screening

Study eligibility will be based on the following criteria:

- i. *Inclusion* 1) housed in K6G unit, 2) ages 18-44 years, 3) screens positive for SUDs via Project START, 4) reports condomless sexual intercourse with a male or male-to-female transgender woman in the six months prior to jail entry, 5) is likely to be remain custody for at least four more days, but less than 45 days based on scheduled court dates, current sentence, etc., 6) has not received an HIV diagnosis (based on self-report), and 7) plans to reside in Los Angeles County following jail release.

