A locator form (See **Contact Information Form**) will be used to determine where and how we should attempt to reach participants post release in order to contact them for follow-up surveys and Peer Mentor meetings. In addition, participants will be encouraged to contact the study's phone number or e-mail following their release from custody. Release dates will be solicited during the interview and tracked on publicly available inmate locator websites in order to establish target dates for the follow-up interviews. so the study team may reach them for follow-up once they are released from jail. On the **Contact Information Form**, participants will be asked to designate whether or not messages may be left and how they want study team members to refer to the study when leaving messages with their indicated contacts.

Participants will also complete a **Release of Information Form**, authorizing release of information from Project START for any substance use disorder assessments conducted with the participation and information on utilization of their services, including case management services following release.

4. Assessments

The baseline surveys will occur in the Men's Central Jail in Los Angeles and will be conducted by a trained research assistant. Participants will complete a 75-minute survey in a classroom, office, or other similar semi-private location. The survey covers the following topics: 1) demographics, 2) criminal justice history and status, 3) HIV/STI knowledge, risk perception, 4) medical mistrust, 5) substance use, 6) self-efficacy and readiness/motivation, 7) service utilization and needs, 8) sexual risk behaviors, and 9) health conditions. Some questions are asked during both interviews, others during only the baseline or specific follow-up interviews.

In addition, we will collect basic information on participants' current and prior arrests (e.g., reason, date, location, length of jail stay) from the publicly available LASD inmate locators (https://app4.lasd.org/iic/ajis_search.cfm) and link this information with the survey data. By matching survey participants with these data, we will augment the surveys with accurate record-based information on participants' criminal justice involvement.

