### *Exploratory subgroup analyses.*

Subgroup analyses will be conducted to understand how the intervention works. We will consider all of our predictors listed in the previous paragraph first as main effects and then as moderators to understand how predictors affect outcomes and how intervention effects possibly differ by groups defined by key predictors. For example, we will examine whether the intervention works well for meth users, but not for non-meth-users or works better for one race/ethnicity group over another. We will plot empirical summary plots (defined above) for all predictors for outcomes to understand predictor main effects on outcomes prior to subgroup analysis. Thus, for example, we will test for main effects for meth use and if present, we will attempt a multivariable model with meth-by-intervention group interactions.

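### The SAP's secondary models cut age at 30 and collapse ASAM level to two groups without a reason; age in years would keep roughly a quarter to a third more of the information if age effects are near linear

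*SAP*

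**What the plan says.** The SAP, under Modeling Issues and Sensitivity Analyses, sets out a model for non-attendance: "We will analyze missing visits as a binary outcome with logistic random intercept regression model". The candidate predictors are offered as examples, and they include "age under 30 vs. 30+; type of SUD; ASAM Level I & II vs. III & IV". The SAP gives no reason for cutting age at 30 or for pairing the ASAM levels, and plans no full-scale version of either.

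These predictors are then used in three ways:
- **Sensitivity analyses, by missingness.** "Variables that are significant predictors of missing visits will be included as predictors in sensitivity analyses of intervention effects".
- **Sensitivity analyses, by imbalance.** The same section checks randomization by one-way ANOVA of the key baseline predictors and carries forward any that differ by arm.
- **Exploratory subgroup analyses.** "We will consider all of our predictors listed in the previous paragraph first as main effects and then as moderators".

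On what is measured, Protocol section 1 (Recruitment and screening) admits "ages 18-44 years", and section 4 (Assessments) says "The survey covers the following topics: 1) demographics". That age is held in years is an inference from these, though a safe one, since eligibility cannot be checked otherwise. Each participant's recommended ASAM level is needed to score the Aim 3 outcomes.

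The primary models (SAP, Modeling Outcomes) contain a mean for each arm at each follow-up time, plus a baseline mean for Aim 3. Neither age nor ASAM level is in them.

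**The concern.** A cut at 30 treats an 18-year-old and a 29-year-old as alike, and a 29-year-old and a 30-year-old as different. If the chance of missing a visit, or the response to the intervention, changes gradually with age, the cut discards part of that signal. Pairing ASAM levels does the same to an ordered scale.

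Three things are at stake, all secondary. The screen for predictors of missing visits becomes weaker, so age is less likely to enter the sensitivity models by that route. When the cut version does enter, age differences within each group stay unadjusted. The moderator tests lose power. The SAP's worked example in the subgroup section looks for a main effect before attempting the interaction, so under that sequence a weaker coding costs power at both steps.

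**Working it through.** **The plan's own figures.** The SAP gives no power for the missing-visit, age, ASAM or moderator analyses, so there is no stated figure to reproduce. Its nearest figure is .80 power for a pairwise arm comparison (a difference of 0.17 at 133 per arm, or 0.20 at 100). That reproduces: the minimum power over the control rates tried is .795 and .812. The .80 used below is a benchmark for a test of age. It is assumed, not taken from the plan.

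**Inputs.** Ages 18-44 (Protocol section 1) give 27 whole years, 12 below 30 and 15 at 30 or above. The cut is from the SAP. The age distribution is not given, so several shapes are assumed. The age effect is assumed linear on the logit scale. Tests are two-sided at .05.

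**Step 1: information kept.** With a linear effect, the share kept is the squared correlation between age and the indicator of age 30 or above:

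share kept = p(1-p) × (difference in group mean ages)² / variance of age.

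For uniform ages, p = 15/27 = .556, the group means are 23.5 and 37, and the variance is (27² - 1)/12 = 60.67. The share kept is (.556 × .444 × 13.5²)/60.67 = 45/60.67 = .742, so 25.8% is lost.

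**Step 2: power with the cut.**

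power = Φ[(1.96 + z) × √(share kept) - 1.96], with z = .8416 for .80.

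For uniform ages: Φ(2.8016 × .861 - 1.96) = Φ(.453) = .675.

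| Assumed ages | Information lost | .80 becomes |
|---|---|---|
| Uniform 18-44 | 25.8% | .675 |
| Bell-shaped, centred 28-31, SD 6-8 | 31-34% | .625-.641 |
| Normal, cut at its median | 36.3% | .608 |

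The loss is 12.5 to 19.2 points. From a .90 benchmark (z = 1.2816), uniform ages give .797 and the median-cut normal gives .734, a loss of about 10 to 17 points. If the cut falls well off-centre (mean age 26 or 35), 41-47% is lost and .80 becomes .57 or .53.

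**Step 3: check by simulation.** Single-observation logistic models, uniform ages, 266 participants, 2,000 replicates:

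| True age effect | Linear age | Cut at 30 |
|---|---|---|
| Linear, main effect | .81 | .66 |
| Linear, age-by-arm interaction | .88 | .76 |
| Step at 30, main effect | .55 | .69 |
| Step at 30, interaction | .67 | .79 |

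The ranking depends on the shape of the true effect. The simulated interactions are large. In a separate run with 200 participants, an interaction log odds ratio of 0.5 per 10 years gave .26 for linear age and .19 for the cut, and 0.3 gave .13 for both.

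**Step 4: what a curvature term would cost.** The noncentrality for .80 on one degree of freedom is 2.8016² = 7.85. A joint two-degree-of-freedom test at that value has power .71, not .80. Against .61-.68 for the cut, the gain is .71 - .68 = 3 points to .71 - .61 = 10 points. From .90 the joint test has .84.

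**Step 5: ASAM level.** Scored 1 to 4 with equal spacing, pairing the levels loses 20% of the information if the four levels are equally common and 24-48% under other assumed mixes. The documents give neither the mix nor any basis for equal spacing.

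**The case against.** The strongest reply is that this is a small matter. The predictor list is introduced as an example, the subgroup work is labelled exploratory, and groups are natural for describing who benefits. The primary models do not use these variables. All of that stands and sets the low weight of the point. The cut codings are nevertheless the only ones written down, and the subgroup section refers back to them.

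A second reply is that the losses rest on assumptions. That is also right: linearity, the age distribution and the .80 benchmark are all assumed, and a step at 30 favours the cut. Nothing in the documents suggests such a step.

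Three stronger readings are tempting and are not supported:
- **That the cut decides whether age is adjusted for at all.** The SAP has a second route: predictors that differ by arm also enter the sensitivity analyses.
- **That the adjusted intervention effect is materially biased.** Unadjusted variance in age is not bias. In simulated complete-case data with age affecting both outcome and missingness (log odds ratio 0.5 per decade each, true arm odds ratio 2.72), the estimate was 2.71 with the cut and 2.74 with linear age. With strongly arm-dependent missingness it was 2.76 and 2.73. These differences are about 1%.
- **That any full-scale coding recovers 12-19 points.** That figure compares the cut with a single linear term. A joint test with curvature recovers about 3-10 points.

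The SAP's own argument against a 90-day threshold for Aim 2 concerns an outcome, so it gives only loose support here.

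**Conclusion.** The point holds as a low-cost improvement to the missing-visit, sensitivity and exploratory models. Neither cut has a stated reason. If age effects are roughly linear, and for uniform to bell-shaped ages with the cut near the centre, cutting at 30 discards about 26-36% of the information on age. A test with an assumed .80 power then falls to about .61-.68. A badly off-centre cut would cost more, and a true step at 30 would make the cut the better coding. For modest interactions the moderator tests are weak under either coding. No figure can be given for ASAM without assuming its level mix and spacing. The relative loss on age does not depend on whether the sample is the protocol's 266 or the SAP's 399.

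**What to change.** In the SAP's Modeling Issues and Sensitivity Analyses section, enter age in years as a linear one-degree-of-freedom term. Use that form in the missing-visit model, the sensitivity models, and the main-effect and interaction tests of the subgroup section. Add a spline or quadratic term only as a secondary check, not as part of the test. Where numbers permit, enter ASAM at its recorded levels, as an ordered score or as categories, merging sparse levels. Keep the two-group versions for plots and tables. If the sponsor prefers the cuts in the models, the SAP should say why.

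The cost is a line of wording, with no new data or staff. Age results would be quoted per 10 years instead of for two groups, and some power would be lost if the true effect is a step at 30.

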### *Modeling Outcomes.*

Each outcome will be analyzed in longitudinal intention to treat using analyses of all available data from Baseline and 3-, 6-, and 12-month follow-up interviews, mobile app, and abstracted record data on utilization, as appropriate. For PrEP cascade outcomes from aim 1, the model is a logistic generalized linear mixed model (GLMM) with a random intercept for participants and a binary 0-1 outcome with 1 indicating success (screening for PrEP say) and 0 indicating a lack of success (not screening for PrEP). We generally do not expect participants to have any PrEP-related positive outcomes at baseline, and we anticipate using only follow-up data at 3, 6 and 12 months in the analysis of specific Aim 1 outcomes. The fixed effects will be a mean for every date (3, 6, 12 months) for each intervention group, for a total of 9 parameters. The first hypothesis is a test for each outcome of differences at 6 months; secondary tests are for differences at 3 months and at 12 months. If the three groups are different at a given time point, we will do pairwise comparisons among the treatments, particularly between the two intervention arms with and without PMs. Specific Aim 3 is similar, though there may be some participants with appropriate SUDs treatment prior to baseline, thus we will include the baseline observation as part of the outcome. At baseline, groups have not been affected by interventions, thus all groups will be the same, so there is one additional parameter for the baseline mean. Otherwise, the analysis is similar to Aim 1 outcome analyses.

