### *Power Calculations.*

For each of the 11 primary outcomes, we calculated power given the Principal Investigator's (PI) estimates of probabilities of success for the 6-month outcomes for each intervention arm. These estimates were based on the existing literature and on preliminary data from the Passport to Wellness study. The PI often specified ranges, in which case we calculated power for the low end and the high end of the ranges resulting in 16 power calculations. Power for the full sample of 399 for testing  $H_0$ : *all arms have the same probability of success*, with a chi-square with 2 degrees of freedom (df) was almost always 1 to three decimal points for alpha=.05; the lowest power was .958 for probabilities of success for the three arms of (0.025, 0.075, 0.15). Some other examples of triples of probabilities we considered were (0.2, 0.6, 0.8), (0.2, 0.45, 0.55), (0.3, 0.5, 0.65). However, we expect a fair amount of loss to follow-up, so we also calculated power for 25% attrition, leaving 100 per group. Again, power is strong, but the lowest power for testing this  $H_0$  is now 86.

Second, we also considered power for comparing between the two intervention groups for testing  $H_0$ : *both intervention arms have the same probability of success*: across a wide range of baseline probabilities, we have 0.8 power at alpha=.05 to detect a difference of 0.17 at n=133, and a difference of 0.20 at n=100 (accounting for loss to follow up) in each group. Because we will be fitting longitudinal models with more data than what goes into a chi-square test, we will have increased power over this basic chi-square test on 2 df.

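### The primary models leave out the baseline variables that the SAP expects to predict missing visits, and adjustment is left to sensitivity analyses whose covariates are picked by unreliable significance screens

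*SAP*

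**What the plan says.** **Primary model.** For Aim 1 the SAP (Modeling Outcomes) specifies a logistic mixed model with a participant random intercept: "The fixed effects will be a mean for every date (3, 6, 12 months) for each intervention group, for a total of 9 parameters". That is 3 arms × 3 visits, with no covariates. Aim 2 uses the same structure in a Poisson model. The data rule is "Each outcome will be analyzed in longitudinal intention to treat using analyses of all available data", and the main time point is set by "The first hypothesis is a test for each outcome of differences at 6 months".

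**Baseline outcome.** For Aim 1, "we anticipate using only follow-up data at 3, 6 and 12 months in the analysis of specific Aim 1 outcomes". For Aim 3 the baseline observation enters as part of the outcome.

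**Missing visits and covariates** (SAP, Modeling Issues and Sensitivity Analyses). The SAP states that "Predictors predictive of missingness are likely to occur". It then plans two screens:
- A logistic regression of missed visits on baseline predictors, after which "Variables that are significant predictors of missing visits will be included as predictors in sensitivity analyses of intervention effects".
- A balance check in which "we analyze the key baseline predictors as outcomes in a one-way ANOVA". Variables that differ by arm also go only into sensitivity analyses.

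The SAP gives no significance threshold. The candidate predictors are listed as examples, and arm is not named as a term in the missing-visit regression. Multiple imputation is reserved for missing baseline predictors. The missing-data assumption behind the primary model is not stated.

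**Expected loss** (SAP, Power Calculations): "we also calculated power for 25% attrition", which leaves 100 per arm.

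**The concern.** A likelihood-based mixed model fitted to all available data handles missed visits correctly if missingness is ignorable given what the model contains: arm, visit and the participant's own observed outcomes. The SAP expects baseline variables to predict missed visits, yet keeps them out of that model. If such a variable also predicts the outcome, and missingness differs by arm, the primary 6-month contrast is shifted while the analysis that would correct it is labelled a sensitivity analysis.

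The selection method adds a second problem. Whether a variable is adjusted for depends on p-values for missingness or for imbalance. The first can easily overlook a real predictor of missingness. The second will flag chance differences, and it treats participants as individually randomised although the protocol (Section 6, Randomization) assigns whole recruitment weeks or months. Neither asks whether the variable is related to the outcome, which is what matters for bias and precision. The adjusted set therefore cannot be known until data are in hand.

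**Working it through.** **1. The SAP's own figures.** The SAP gives no figure for covariate adjustment or for bias from missed visits, so its power figures are the only ones to reproduce.
- Attrition: 133 × 0.75 = 99.75, the stated 100 per arm.
- Lowest three-arm power, success 0.025/0.075/0.15, by simulation: 0.948 (likelihood ratio) or 0.941 (Pearson) at 133 per arm, against 0.958 stated; 0.872 or 0.848 at 100 per arm, against 86% stated.
- Pairwise worst case: 0.795 for a difference of 0.17 at n=133 and 0.812 for 0.20 at n=100, against 0.8 stated.

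These agree within 2 points. The SAP's three arms total 399 and the protocol's two arms total 266, so both sizes are used below.

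**2. Chance that the missing-visit screen flags a real predictor.** Assume a binary predictor present in half the sample and one visit, with n per predictor group (199.5 or 133):

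z = [d − 1.96·√(2p̄(1−p̄)/n)] / √[(p₁(1−p₁)+p₂(1−p₂))/n]

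For 20% versus 30% missing, d = 0.10 and p̄ = 0.25 (25% overall, as the SAP assumes):
- n=199.5: (0.10 − 1.96×0.0434)/0.0431 = 0.35, power 0.64.
- n=133: (0.10 − 1.96×0.0531)/0.0527 = −0.08, power 0.47.

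For 22% versus 28%, power is 0.28 and 0.20.

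The planned regression pools three visits, which helps unless the same people miss every visit. With an assumed within-person correlation of 0.5, the effective n rises by 3/(1+2×0.5) = 1.5. For 20% versus 30%, power becomes about 0.81 at N=399 (n≈299) and 0.64 at N=266 (n=199.5). The one-visit figures correspond to a correlation of 1.

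**3. False flags from the ANOVA screen.** The SAP lists eight example predictors. Taken as independent tests at 0.05 under sound randomisation: 1 − 0.95⁸ = 0.34. The 0.05 threshold is an assumption here, and assignment by period is not reflected.

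**4. Bias from omitting a predictor.** The documents give no associations. Assumed: a binary predictor with 50% prevalence; 15% versus 35% missing (25% overall); odds ratio with the outcome of 1, 2 or 4.

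*Closed form, one visit, observed cases.* The observed rate in an arm is (p₀(1−m₀)+p₁(1−m₁))/(2−m₀−m₁). With success 0.20 versus 0.45 and odds ratio 4, the strata are 0.098/0.302 in control and 0.285/0.615 in intervention.
- Same missingness in both arms: control (0.098×0.85+0.302×0.65)/1.5 = 0.186, intervention 0.428, difference 0.242; bias −0.008.
- Predictor-linked missingness in control only (25% throughout in intervention): 0.450 − 0.186 = 0.264; bias +0.014.
- Linked in opposite directions: 0.472 − 0.186 = 0.286; bias +0.036.
- Predictor unrelated to outcome (odds ratio 1): bias 0 in every pattern.

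*The planned type of model.* A random-intercept logistic model with arm-by-visit means was fitted to 300,000 simulated participants in two arms, with outcome odds ratio 2 or 4, under the null and with a true difference of about 0.27. Fitted minus true 6-month risk difference:

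| Missingness pattern | Without predictor | With predictor |
|---|---|---|
| Same in both arms | about 0 under the null; at most 0.004 in size otherwise | about 0 |
| Linked to predictor in one arm | +0.005 to +0.017 | about 0 |
| Opposite directions (extreme) | about +0.01 to +0.03 | about 0 |

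With the predictor, deviations are at most 0.002, which is simulation error. The sign follows the assumed direction and would reverse if the predictor worked the other way.

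**5. Effect on the test.** Under the null at 0.30 with 100 observed per arm, SE = √(2×0.3×0.7/100) = 0.065. The observed-case biases at that rate are 0.0096 to 0.0366, or 0.15 to 0.56 SE. These move a nominal 5% rejection rate to 5.3% to 8.7%. With the same missingness in both arms it stays at 5%.

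**The case against.** An unadjusted primary analysis with adjusted sensitivity analyses is a recognised choice in a randomised trial. The mixed model also borrows from each participant's other visits. Retention effort covers both arms (protocol, Sections 9 and 11): monthly payments for contact, control contact attempts every 2 to 4 weeks, tracing, and interviews on reincarceration. Abstracted records may supply an outcome when an interview is missed. The missing-visit screen runs before the final analysis and does not look at treatment effects, and the SAP separately explores the predictors' main effects on outcomes.

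Much of this stands, and it limits the size of the problem. It does not justify choosing covariates by p-value. The retention measures do not equalise the arms: intervention participants also meet mentors every one to two weeks for the first 8 weeks (Section 8a), and the app, one of the SAP's data sources, is given to that arm only. The planned missing-visit model names no arm term, so it may not show whether loss differs by arm.

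A reader might go further and infer that the primary estimate rests on an assumption the SAP itself expects to fail, or that the primary result is the less credible of the two planned analyses. The documents do not support either. The SAP predicts only that some variables will be related to missing visits. It does not predict that they affect the outcome beyond the observed visits, or that missingness differs by arm.

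Examples with larger bias are easy to build. Take success of 0.15/0.45 in control and 0.40/0.70 in intervention in two equal strata, with visits missed by 45%/15% in control and 20%/20% in intervention. The observed difference is then 0.55 − 0.332 = 0.218 against a true 0.25. Those rates are invented, and the calculation uses one visit. With 35%/15% in both arms the observed rates are 0.32 and 0.57, and the bias disappears.

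**Conclusion.** The concern holds as a weakness in how adjustment is specified. The primary models omit variables that the SAP expects to predict missing visits, the missing-data assumption is unstated, and the adjustment set depends on screens that can readily miss a real predictor or flag a chance imbalance.

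The expected bias is small: about zero without both an outcome link and arm-dependent missingness, roughly 0.005 to 0.017 if both are present in the forms assumed, and up to 0.03 in the extreme. These sizes depend on assumed associations, not on trial data. Both conditions are plausible here, since prior HIV testing is close to the Aim 2 outcome and contact with study staff differs by arm, but the documents do not state them. Aims 1 and 2 are the most exposed. Missingness that depends on unobserved outcomes is a separate question that covariates do not settle.

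**What to change.** In the SAP, Modeling Outcomes and Modeling Issues and Sensitivity Analyses:

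1. Pre-specify two or three baseline covariates, already collected, for the primary models: for example baseline behaviour such as prior HIV testing, stimulant use and ASAM level. Report the unadjusted model as the sensitivity analysis.
2. Do not select covariates by the ANOVA or by missing-visit p-values. Describe baseline balance without tests.
3. Include arm and arm-by-predictor terms in the missing-visit model, and use it to describe loss.
4. State that the primary analysis assumes missingness is ignorable given arm, visit, these covariates and observed outcomes.
5. Report standardised risk differences alongside odds ratios, because adding covariates changes what a conditional odds ratio means.

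The cost is SAP wording, a few model terms and slightly more complex fitting. The list must stay short. At the SAP's lowest success rates with 100 per arm there are only about 100 × (0.025+0.075+0.15) = 25 events over three arms, or 17.5 over the outer two. The SAP should therefore name in advance a reduced set, or none, for outcomes that rare.
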